### 7.8.3 Additional Immunogenicity Endpoint(s)

CCI

## 7.9 Pharmacokinetic/Pharmacodynamic Analysis

{Not applicable}

## 7.10 Other Outcomes

{Not applicable}

## 7.11 Safety Analysis

All summaries and analyses of safety data are based on subjects in the Safety Analysis Set. Unless otherwise specified, the safety data will be summarized according to the treatment arms,

CONFIDENTIAL

(ie, according to the formulation arms, separately for the 1 and 2 (or 2 and 3) dose groups), for each age stratum, and overall within each cohort.

### 7.11.1 Adverse Events

#### In-Clinic Assessments of Reactogenicity

In-clinic 30-minutes post-vaccination assessments of reactogenicity AEs include local events (injection site pain, erythema/redness, induration, and swelling) and systemic events (headache, fatigue, myalgia, arthralgia, vomiting [number per day/intensity] and diarrhea [number per day/consistency] for children aged 4 to <9 years; and irritability/fussiness, drowsiness, loss of appetite, vomiting [number per day/intensity], and diarrhea [number per day/consistency] for children aged 6 weeks to < 4 years). Severity of injection site pain and of the systemic events is assessed in-clinic as mild, moderate or severe according to Protocol Tables 9a (age 4 – 9 years) and 9b (age 6 weeks to <4 years). Measurements of the largest diameter for injection site erythema/redness, swelling, and induration are collected. These measurements will be used to derive severity grades based on the criteria included in [Appendix A](#) and [Appendix B](#).

Temperature measurements are also collected and a systemic event of ‘fever’ will be derived as Yes/No based on temperatures  $\geq$  38 degrees centigrade [3]. Temperature levels will also be categorized in 0.5 degree intervals (centigrade). Number and percent of subjects with reactogenicity events 30-minutes post vaccination will be summarized for each vaccine administered, for each local and systemic event, and by severity.

#### Subjects’ Legal Guardian Assessments of Reactogenicity via Subject’s Diary

Reactogenicity is also assessed by the subject’s legal guardian for 7 days following each vaccination (day of vaccination and the following 6 days) via diary collection of solicited AEs. These include local events (injection site pain, erythema/redness, induration, and swelling) and systemic events of headache, fatigue, myalgia, arthralgia, vomiting (number per day/intensity), and diarrhea (number per day/consistency) for children aged 4 to <9 years; and irritability/fussiness, drowsiness, loss of appetite, vomiting (number per day/intensity), and diarrhea (number per day/consistency) for children aged 6 weeks to < 4 years. Measurements of the largest diameter for injection site erythema/redness, swelling, and induration are collected. These measurements will be used to derive severity grades based on the criteria presented in [Appendix A](#) and [Appendix B](#). Temperature measurements are also collected and a systemic event of ‘fever’ will be derived as Yes/No based on temperature  $\geq$  38 degrees centigrade. Temperature levels will also be categorized in 0.5 degree intervals (centigrade). Severity categories for each solicited AE are defined in Protocol Section 9.1.7. In addition, the relationship of solicited systemic symptoms occurring within 7 days after each vaccination is assessed by the investigator during diary review.

For each solicited AE, the percentage of subjects will be summarized by event severity for each day for the 7 days following vaccination (including the day of vaccination) and overall within the 7 days following vaccination. In addition, summaries will be provided for the intervals of Days 1 to 3 and Days 4 to 7 following each vaccination. For subjects with more than 1 episode of the

same event within an interval (overall within the 7 days following vaccination, days 1-3, and days 4-7), the maximum severity will be used for tabulations.

The relationship of solicited systemic symptoms occurring within 7 days after each vaccination will also be tabulated. If a subject reported more than one episode of the same event, then the strongest relationship will be included in the summaries.

A summary of the day of first onset of each event with intensity grade mild or higher and the number of days subjects reported experiencing each event with intensity grade mild or higher will also be provided for each vaccination. The number of days a subject reported experiencing a symptom is calculated as the total of all days the subject reported the symptom, regardless of whether the symptom was reported on consecutive days (eg, a headache reported on Day 1, Day 3, and Day 4 would be included with a duration of 3 days).

For all summaries by each vaccination, summaries after any vaccination will also be included.

#### Unsolicited AEs

Unsolicited AEs will be coded using the MedDRA, Version 17.0 or later.

All unsolicited AEs will be collected for 28 days following each vaccination. To attain 28 full days, all AEs with onset on the day of vaccination (day 1 relative to the given vaccination day) through day 29 relative to the given vaccination day will be included. SAEs and AEs leading to subject withdrawal from the trial will be collected throughout the trial.

Unsolicited AEs will be assigned to vaccine dose (1st, 2nd or 3rd, if applicable). All summaries described in this Section will be generated by vaccine dose number. Summaries by each vaccination will also include summaries after any vaccination

The incidence of AEs will be summarized by SOC and PT by presenting the number and percentage of subjects with an AE. A subject will be counted only once within each SOC and within each PT, or the overall category. Separate summaries will be provided for AEs by maximum severity (mild, moderate, severe) and relationship (not related, related) to study vaccine. If a subject reported more than one AE within a SOC or PT, then the AE with the highest known severity or strongest relationship within each SOC and each PT will be included in the summaries by severity or relationship, respectively. These summaries will generally be presented in the following 3 ways: 1) overall up to 28 days after each vaccination, 2) with onset between 1 and 7 days after each vaccination, and 3) with onset between 8 and 28 days after each vaccination.

In addition, the incidence of AEs will be summarized by SOC and by PT separately. Vaccine-related AEs and vaccine-related AEs by maximum intensity will be summarized by SOC and PT. These summaries will be provided for events occurring up to 28 days after each vaccination.

In addition, for each group, *most frequent* unsolicited AEs (with frequency of preferred term greater than 5% and with a minimum of two subjects in any of the 8 formulation/dose combination groups) will be summarized (number/percent of subjects with the event) up to 28 days after either vaccination by SOC and PT. This summary will also be done for *most frequent* non-serious events (presenting both number of events and number/percent of subjects with the

event). The number of most frequent non-serious events will also be presented. Note that the summaries of most frequent non-serious events are being prepared only for trial results disclosure requirements and will not necessarily be addressed in the clinical study report (CSR).

The incidence of AEs leading to investigational vaccine withdrawal will be summarized by SOC and PT after each vaccination and for the entire study duration (including all events leading to withdrawal with onset after the first vaccination dose through the end of the study).

The number of SAEs and number/percent of subjects experiencing SAEs will be summarized by SOC and PT after each vaccination and for the entire study duration (including all reported SAEs with onset after the first vaccination dose).

In addition to the overall AE listing, separate listings for SAEs, AEs leading to subject withdrawal from the trial, AEs resulting in death will be provided

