#### Baseline Definition and Windowing Conventions

Study Day 1 is defined as the date of the first vaccination, as recorded on the eCRF vaccination page. Other study days are defined relative to Study Day 1, with Day -1 being the day prior to Day 1. In addition, day relative to vaccination will be derived for each vaccination dose. For example, day relative to the first dose will be equal to the Study Day. Day relative to the second dose will start with a value of 1 on the day of the second dose and so on for each vaccination given. Day relative to dose is of use for tables presenting summaries of events relative to dose.

For listings presenting observations or events by day, both the Study Day and Day Relative to Dose will be presented.

Baseline is defined as the last non-missing measurement taken before the first dose of vaccination (Day 1), unless otherwise defined for a particular endpoint parameter.

A windowing convention will be used to determine the analysis value for a given study visit for observed data analyses. The window definitions as outlined below in [Table 7.a](#) and [Table 7.b](#) will be used for the immunogenicity (serology and CMI) and vital signs, respectively. The window conventions are:

1. A window of +/- 7 days from the target day is applied to the following visits: Study Days 29 and 57 for cohort 1 and Study Days 56, 84, 112, and 140 for cohort 2;
2. A window of +/- 28 days from the target day is applied to the following visits: Study Day 210 for cohort 1 and Study Day 293 for cohort 2.

The windows for immunogenicity are constructed by dosing period relative to actual dosing day. Windows for vital signs are constructed relative to the actual study day.

One or more results for a particular immunogenicity or vital sign variable may be obtained in the same visit window (see study window definitions in [Table 7.a](#) and [Table 7.b](#)). In such an event, the result with the date closest to the expected visit date will be used. In the event that 2 observations are equidistant from the expected visit date, the later observation will be used.

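### Unsolicited AEs starting on relative day 29 fall in neither interval table, and in Cohort 1 that day can belong to two doses with no rule to choose between them

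*SAP*

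**What the plan says.** SAP 7.11.1 (Unsolicited AEs) opens with the nominal period: "All unsolicited AEs will be collected for 28 days following each vaccination". To make that 28 full days, it takes onsets from the day of vaccination, which it numbers day 1, and continues "through day 29 relative to the given vaccination day will be included".

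The summaries are then presented three ways: overall, "with onset between 1 and 7 days after each vaccination", and "with onset between 8 and 28 days after each vaccination". Protocol 13.1.4 lists the same three ways but does not mention day 29, so the extension to day 29 comes from the SAP while the interval limits were left as they stood.

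Each event is to be assigned to a dose, and "All summaries described in this Section will be generated by vaccine dose number". A summary after any vaccination accompanies the by-dose ones.

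The day numbering is in SAP 7.1 (Baseline Definition and Windowing Conventions): "day relative to the first dose will be equal to the Study Day", and the count restarts at 1 on the day of dose 2. SAP 4.4 places the Cohort 1 injections on Days 1 and 29 and the Cohort 2 injections on Days 1, 56 and 112. In the Cohort 1 1-dose arms the Day 29 injection is saline.

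**The concern.** Two things do not fit. The interval tables should partition the overall window, but their limits add up to one day fewer. And the last day of the dose 1 window is, under the planned Cohort 1 schedule, the first day of the dose 2 window, while the SAP requires every event to go to a dose.

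Unsolicited events in the 28 days after each vaccination are a primary safety endpoint (Protocol 5.2.1, SAP 5.1) and bear on the choice of formulation. Two programmers could both follow the SAP and produce different by-dose and by-interval tables. In the 1-dose arms the choice of dose decides whether an event is tabulated after vaccine or after saline.

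**Working it through.** **Inputs**
- Overall window: relative days 1 to 29 (SAP 7.11.1).
- Interval tables: 1 to 7 and 8 to 28 (SAP 7.11.1).
- Relative day equals Study Day for dose 1 and restarts at 1 at each later dose (SAP 7.1).
- Cohort 1 dose 2: Day 29, visit window +3, so Study Days 29 to 32 (SAP Tables 4.a and 4.b). Cohort 2 doses: Days 1, 56 and 112.

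**1. The plan's own figure.** Elapsed days from relative day 1 to relative day 29: 29 − 1 = 28. The 28 full days is reproduced. Counted inclusively, the window holds 29 − 1 + 1 = 29 calendar days. The 29-day window is therefore not an error in itself.

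**2. Coverage by the interval tables.** First interval: 7 − 1 + 1 = 7 days. Second: 28 − 8 + 1 = 21 days. Total 7 + 21 = 28, so 29 − 28 = 1 day is uncovered. Read as relative days, the tables cover 1 to 28 and miss day 29. Read as days elapsed (relative day = elapsed + 1), they cover 2 to 29 and miss day 1. The SAP's numbering supports the first reading (see the objection).

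**3. Overlap between doses.** If dose 2 is on Study Day *d*, its window runs from *d* to *d* + 28.

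| Cohort 1, dose 2 on | Dose 1 window | Dose 2 window | Shared days |
|---|---|---|---|
| Day 29 | 1–29 | 29–57 | Day 29 |
| Day 30 | 1–29 | 30–58 | none |
| Day 31 | 1–29 | 31–59 | none |
| Day 32 | 1–29 | 32–60 | none |

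In Cohort 2 the windows are 1–29, 56–84 and 112–140, with no shared day. The Cohort 1 overlap arises on the planned day, and Protocol 7.3 advises booking later vaccination visits early in their window.

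**4. Is there a rule for the shared day?** The dose-association rules in SAP 7.1 (Missing or Partial Dates) apply only when the onset date is missing or incomplete. They can themselves place an onset on an injection date: an event with neither date is given the last vaccination date. For a complete onset date nothing is stated. Protocol 10.2.1.1 lists start and end dates for each event, not a start time, so an onset before the injection cannot in general be told from one after it.

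**5. Which onsets leave the interval tables.** Relative day 29 is Study Day 29 + 28 = 57 for a Cohort 1 dose 2 given on Day 29. In Cohort 2 on schedule it is Study Days 1 + 28 = 29, 56 + 28 = 84 and 112 + 28 = 140. For Cohort 1 dose 1 on schedule, the outcome depends on the missing rule. If the Day 29 event goes to dose 2, it appears in that dose's 1-to-7-day table. If it goes to dose 1, it appears in neither of dose 1's interval tables.

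**6. Scale.** One day in 29 is 3.4% of the window's days; this is a share of days, not of events. With about 15 subjects per formulation/dose combination per Cohort 1 group, moving one subject changes a by-dose percentage by 1/15 = 6.7 percentage points.

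**The case against.** The best defence is that the SAP defines its 28 days as running through day 29. Carry that definition into the second interval and it becomes 8 to 29, which completes the partition: 7 + 22 = 29. That is a natural reading, but the SAP does not write it, and literal programming of 8 to 28 gives a different table.

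On attribution, SAP 7.1 does say that events should be tied to the correct dose as far as possible, and one of its examples places an uncertain onset on the date of the second vaccination. This suggests that an injection-day onset goes to that day's dose. It is an analogy from the rules for missing dates, not a rule for known ones.

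Three stronger readings are tempting, and the documents do not support them.
- A reader might infer that vaccination-day events vanish from the 1-to-7-day table. That needs the elapsed-day reading. SAP 7.1, the solicited-event text in 7.11.1 and the unsolicited-event text itself all count the vaccination day within their day numbering, as day 1 or as the first of the 7 days.
- A reader might infer that events are counted twice. Assignment to a dose points to one dose per event, and a subject is counted once per term in the summary after any vaccination.
- A reader might take all 480 Cohort 1 children as affected. That is a ceiling on children, not a count of events. The problem needs dose 2 on exactly Day 29 and an onset that same day.

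The Day 1-28 and Day 28-56 entries in the Cohort 1 schedule tables do not settle the matter either way. They are collection rows, not analysis windows.

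**Conclusion.** The point holds as an internal mismatch with limited reach. On the SAP's relative-day convention, day-29 onsets are in the overall table and in neither interval table. In Cohort 1 children given dose 2 on Study Day 29, that day lies in both dose windows and no rule assigns a complete-date onset. Misattribution is a possibility left open, not something the SAP prescribes. It matters most in the 1-dose arms, where it can move an event between vaccine and saline.

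No event is lost from the overall 28-day summary, and incidence after any vaccination does not change. What can change is the split by dose and by onset interval. The documents give neither the number of children dosed on exactly Day 29 nor the number of onsets on that day, so the number of affected events cannot be derived. The conclusion assumes that the interval limits are programmed as written.

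**What to change.** Write all unsolicited-AE windows in relative days. Either keep the overall window at 1–29 and make the intervals 1–7 and 8–29 (7 + 22 = 29), or set it to 1–28 with 1–7 and 8–28 (7 + 21 = 28). The second option removes the overlap with a Day 29 dose but gives up the SAP's stated aim of 28 full days.

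Before unblinding, add the same-day rule: the window for a dose ends at the next injection, and an onset on an injection day is assigned to that day's dose unless it is recorded as starting before the injection.

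The cost is two SAP sentences and one derivation line. There is a small downside to state openly. When dose 2 is on Day 29, the dose 1 window becomes 28 calendar days. And because only start and end dates are listed for collection, some onsets that preceded the injection that day will be assigned to dose 2, which is saline in the 1-dose arms.

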### **7.3 Criteria for Delay of Vaccination and Blood Sampling**

After enrollment, subjects may encounter clinical circumstances that warrant a delay in subsequent trial vaccination. These situations are listed below:

- Subjects with a body temperature 38.0°C (100.4°F) or higher within 3 days of intended trial vaccination.
- Subjects who have received antipyretics/analgesic medications within 24 hours prior to the intended vaccine administration.
- Subjects who have received blood, blood products, and/or plasma derivatives or any parenteral immunoglobulin preparation in the past 3 months (prior to initial vaccination).

If the subject cannot be randomized and vaccinated on Day 1 due to a temporary contraindication and must return at a later time, the same identification number (screening number) should be kept. If the subject randomization visit is re-scheduled for more than 15 days after the screening, then a new ICF should be obtained.

For subsequent vaccination visits, it is strongly recommended to schedule them as early in the visit window as possible, in case these visits need to be re-scheduled due to a vaccination and/or blood sampling temporary contraindication.

There are also circumstances under which receipt of further vaccines is a contraindication in this trial. These circumstances include anaphylaxis or severe hypersensitivity reactions following the initial vaccination. If these reactions occur, the subject must not receive additional vaccinations, but is encouraged to continue in trial participation for safety reasons.

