#### Unsolicited AEs

Unsolicited AEs, and SAEs, will be MedDRA coded and summarized by system organ class (SOC) and preferred term (PT) for each formulation arm in each cohort. AEs leading to subject's withdrawal from the trial will also be summarized.

All unsolicited AEs up to 28 days after each study vaccination will be included in the analyses of all AEs. SAEs, and AEs leading to subject withdrawal from the trial collected during the trial will be included.

In general, unsolicited AEs will be tabulated at each of the following levels: overall summary (subjects with at least 1 AE) and by SOC and PT. Subjects reporting more than 1 occurrence for the term (level) being summarized will be counted only once. Unsolicited AEs will be summarized as follows: by PT by SOC and PT, including events with frequency greater than 5% (and as above for subjects with at least 1 AE); by SOC, PT, and severity; and by SOC, PT, and relationship to the investigational vaccine. Unless otherwise specified, unsolicited AEs will be summarized in the following 3 ways: 1) overall up to 28 days after each vaccination, 2) with onset between 1 and 7 days after each vaccination, and 3) with onset between 8 and 28 days after each vaccination.

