### **4.2 Secondary Objectives**

- To evaluate the geometric mean titers (GMT) and geometric mean fold rises (GMFRs) of anti-NoV GI.1 VLP and GII.4 VLP antibody titers as measured by Pan-Ig ELISA.
- To evaluate the seroresponse rate in serum anti-NoV GI.1 VLP and/or GII.4 VLP antibody blocking titers as measured by histoblood group antigen (HBGA) binding assay.
- To evaluate Geometric Mean Blocking Titers (BT50) and GMFR of serum anti-NoV antibody titers for GI.1 VLP and/or GII.4 VLP as measured by the HBGA binding assay.
- To assess safety by the incidence of AEs leading to subject's withdrawal from the trial throughout the trial.

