***Safety***

- Percentage of subjects with any AE leading to subject's withdrawal from the trial - from the day of vaccination through Day 210 (Cohort 1) and Day 293 (Cohort 2).

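### The SAP's only withdrawal-AE table names vaccine withdrawal, whereas the secondary safety endpoint is withdrawal from the trial

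*SAP*

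**What the plan says.** Protocol 5.2.2 and SAP 5.2 give the same single secondary safety endpoint: "Percentage of subjects with any AE leading to subject's withdrawal from the trial". It is counted from the day of vaccination to Day 210 in Cohort 1 and Day 293 in Cohort 2. The objective in SAP 4.2 agrees: "To assess safety by the incidence of AEs leading to subject's withdrawal from the trial throughout the trial". Protocol 13.1.4, under unsolicited AEs, commits to a summary: "AEs leading to subject's withdrawal from the trial will also be summarized".

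SAP 7.11.1, also under unsolicited AEs, states: "The incidence of AEs leading to investigational vaccine withdrawal will be summarized by SOC and PT". The sentence asks for this after each vaccination and over the whole study, with a parenthesis that reads "including all events leading to withdrawal with onset after the first vaccination dose through the end of the study". Later in the same section, AEs leading to withdrawal from the trial are given a separate listing. The section also says that they are collected throughout the trial. No other table of withdrawal AEs is described there. SAP 7.13, which records departures from the protocol, does not mention this difference.

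**The concern.** An endpoint and the table that reports it should name the same event. Here one sentence in the SAP substitutes vaccine withdrawal for trial withdrawal, and the same section uses both terms for different outputs. A programmer who follows it literally would select AEs by the action taken with the vaccine, not by whether the AE ended the child's participation.

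At stake is the one secondary safety endpoint. The only table with a written specification could report a different quantity under a title close enough that a reader of the study report might not notice.

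**Working it through.** The plan gives no figure to reproduce. The check compares the texts and does one subtraction from the visit schedule.

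**Step 1: the event named in each place**

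| Place | Event | Output |
|---|---|---|
| Protocol 5.2.2 and SAP 5.2 | AE leading to withdrawal from the trial | Percentage of subjects |
| SAP 4.2 | AE leading to withdrawal from the trial | Incidence |
| Protocol 13.1.4 | AE leading to withdrawal from the trial | Summary |
| SAP 7.11.1, table | AE leading to withdrawal of the vaccine | Incidence by SOC and PT |
| SAP 7.11.1, listings | AE leading to withdrawal from the trial | Listing |

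Only the table differs.

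**Step 2: whether the events differ in this trial**

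They do. After anaphylaxis or a severe hypersensitivity reaction, protocol 7.3 says "the subject must not receive additional vaccinations, but is encouraged to continue in trial participation for safety reasons". That child has stopped vaccine but has not left the trial. The data items are also separate: protocol 10.2.1.1 records the action taken with the vaccine for each AE, while protocol 7.4 records the primary reason for leaving the trial.

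**Step 3: how much of the endpoint period follows the last injection**

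Inputs: last planned injection on Day 29 (Cohort 1) or Day 112 (Cohort 2), from the schedules of procedures; end of the endpoint period on Day 210 or Day 293, from SAP 5.2. Nominal days are used, and the saline injection is counted as part of the regimen.

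- Cohort 1: 210 − 29 = 181 days; 181 / 210 = 86%.
- Cohort 2: 293 − 112 = 181 days; 181 / 293 = 62%.

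For a child who has had every injection, an AE starting in that window can lead to trial withdrawal but not to vaccine withdrawal.

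**Step 4: how each child is counted under a literal reading**

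| Child | Endpoint | SAP table |
|---|---|---|
| AE stops vaccine and child leaves the trial because of it | Counted | Counted |
| AE stops vaccine, child stays in the trial | Not counted | Counted |
| Fully dosed, leaves the trial for an AE starting after the last injection | Counted | Not counted |

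The last two rows err in opposite directions, so the table's total could be above or below the endpoint's.

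**The case against.** The strongest reply is that this is a slip of wording, and much in the documents supports it.

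- SAP 7.1 says that safety endpoints are summarised descriptively, with frequency and percent for categorical data. Trial withdrawal for an AE is a listed safety endpoint, so that rule covers it. SAP 7.11 supplies the population (Safety Analysis Set) and the layout by arm, age stratum and cohort.
- The parenthesis in the disputed sentence says only withdrawal, and runs to the end of the study. That fits trial withdrawal better than vaccine withdrawal, because no dose remains after Day 29 or Day 112.
- The AEs are collected to Day 210 or Day 293 (protocol 9.1.7) and listed, so the count could be recovered.
- The disposition summary in SAP 7.3 shows primary reasons for discontinuation, and adverse event is one of the recorded categories (protocol 7.4).

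The first three points stand, and they limit the consequence. They do not settle which event the table counts, because the same section uses both terms for different outputs. The disposition summary is no substitute: it covers randomized subjects, takes the primary reason only, joins vaccine regimen and study visits in one phrase, and has no SOC or PT.

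A reader might infer that the endpoint will never be estimated, or that every AE withdrawal after the last injection will be missed. The documents do not support either. SAP 7.1 commits to n and % for the endpoint, and the parenthesis can be read as including those late withdrawals.

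**Conclusion.** The SAP is wrong as written on this point. Its only specified table of withdrawal AEs names a different event from the endpoint, the objective and the protocol's analysis section, and the difference is not declared as a change. It is probably a wording slip.

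The size cannot be stated in subjects. The documents give no expected number of AE withdrawals or of vaccine stops with continued follow-up, so the discrepancy may be small or nil. The 181 days in each cohort show when the two events can diverge; they do not measure bias. The miscounting in the working depends on reading the sentence literally and on the nominal schedule. No data are lost under either reading.

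Nothing here questions the protocol's rules on when vaccination stops.

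**What to change.** Reword the sentence in SAP 7.11.1 along these lines:

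> AEs leading to the subject's withdrawal from the trial will be summarised as number and percentage of subjects, by SOC and PT and by formulation/dose arm, in the Safety Analysis Set, from the first dose through Day 210 (Cohort 1) or Day 293 (Cohort 2).

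Keep the existing listing. If AEs leading to vaccine withdrawal are also of interest, give them a separate table whose title names that event.

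No confidence interval is required. SAP 7.11 plans none for any AE summary, and n and % meet the endpoint definition.

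The cost is one SAP sentence and one table title, plus a second table only if vaccine withdrawal is kept. No new data collection is needed, because these AEs are already collected and listed.
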